8.3. Taste and Palatability Questionnaire

For the subset of participants receiving a new dosage form or switch to a higher dose (i.e., modified dose of voxelotor as dispersible tablets), taste and palatability questionnaires collected on day of switch to the modified dose and 2 consecutive visits will be summarized using descriptive statistics.

8.4. Pharmacokinetics

Pre-dose voxelotor whole blood and plasma concentrations will be available for day of switch to modified dose, 14-day post switch, and 12-week post switch. The PK data will be reported for an individual participant with corresponding voxelotor pre-switch dose, pre-switch formulation, and post-switch voxelotor dose (and formulation) in a table. In addition, the PK data for day of switch, 14-day post-switch, and 12-week post-switch will be summarized (all data and by pre-dose formulation) using descriptive statistics (number of valid PK data, mean, SD, 95% Confidence Interval, median, min, max). Below the limit of quantitation (BLQ) concentrations will be treated as zero for the computation of descriptive statistics. Concentrations assigned a value of missing will be omitted from the calculation of descriptive statistics.

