5. TREATMENTS ADMINISTERED

5.1. Treatments Administered

All participants will receive voxelotor QD, administered orally as tablets, dispersible tablets, or a powder for oral suspension dosage form (packaged as stick packs).

Participants aged \geq 12 years will receive a voxelotor dose of 1500 mg QD administered as 3×500 mg tablets regardless of their body weight.

Participants aged < 12 years will receive a voxelotor dose based on their body weight to provide exposure corresponding to the adult dose of 1500 mg QD. The participant's weight at study entry will be used to determine their starting voxelotor dose in this study, as indicated in Table 1 and Table 2. The dose should be adjusted if the participant's weight increases or decreases at a scheduled clinic visit. The participant's weight will be measured according to the Schedule of Assessments (Appendix A), and dose adjustments made as needed and as indicated in Table 1 and Table 2.

The 1500 mg-equivalent dose in participants aged < 12 years will be administered as powder for oral suspension or as dispersible tablets based on the availability of each formulation.

A bioequivalence study in healthy volunteers (Study GBT-0119) comparing the voxelotor powder for oral suspension and dispersible tablet dosage forms showed that a single dose of the powder for oral suspension had an approximately 35% greater exposure than the same mg dose of dispersible tablets. Therefore, for all participants taking dispersible tablets in this study, the dose of the dispersible tablets will be increased by approximately 35%. This increase allows for a dose adjustment for the dispersible tablets ensuring that all participants taking the dispersible tablet dosage form receive the same exposure as participants receiving the powder for oral suspension dosage form (Table 1 and Table 2).

All participants < 12 years of age will receive the doses shown in Table 1 until sites are instructed by the Sponsor to switch these participants to the modified dispersible tablet doses shown in Table 2 at their next regularly scheduled visit (Appendix A). The date of the switch will be recorded on the dosing electronic case report form (eCRF).

Table 1: Voxelotor (Powder for Oral Suspension or Dispersible Tablet) Weight-Based Doses for Participants Less than 12 Years of Age

Weight	1500 mg-Equivalent Adult Dose
5 to < 10 kg	400 mg
10 to < 20 kg	600 mg
20 to < 40 kg	900 mg
≥ 40 kg ^a	1500 mg

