8.6. Pharmacokinetic Sample Collection and Analysis

Whole blood and plasma concentrations of participants taking the modified dose of voxelotor dispersible tablet will be collected predose on the day participants switch to modified dose dispersible tablet (Day of Switch), 14 days after the switch date (14 Days Post-Switch), and 12 weeks after the switch date (12 Weeks Post-Switch) at select sites (Figure 1, Appendix B). Participants should be encouraged to take their voxelotor dose at a regular time every day. However, on the days of PK sample collection, the PK sample should be obtained approximately 24 hours after the subject's administration of voxelotor. Therefore, the site should instruct the subject to take the dose approximately 24 hours prior to their scheduled visit The participant or their caregiver are to record the time of the voxelotor dose taken prior to each of these visits.

Whole blood and plasma voxelotor levels will be evaluated by comparison of predose voxelotor concentration on 14 Days Post-Switch and 12 Weeks Post-Switch with predose voxelotor concentration on the Day of Switch.

A population pharmacokinetic (PK) analysis may be conducted using nonlinear mixed effects modeling.

Figure 1: Pharmacokinetic Sample Collection

* Day of Switch is a regularly scheduled visit (Day 1 or other) at which participant starts modified dose dispersible tablet.

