7.2 Pharmacokinetic Population

The pharmacokinetic (PK) population is defined as all participants who take at least 1 dose of voxelotor and in whom at least 1 concentration value is reported.

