8. STATISTICAL METHODS

Statistical analyses will be performed using SAS® Version 9.4 or higher.

Continuous variables will be descriptively summarized using number of participants (n), mean, standard deviation (SD), median, minimum, and maximum. Categorical variables will be descriptively summarized by presenting the number (frequency) and percentage in each category. All statistical analyses conducted will be descriptive and no formal statistical tests are planned.

Additionally, for the subset of participants receiving the modified dose of voxelotor in dispersible tablet in this study, separate summaries will be provided for selected CRF data (e.g., TEAEs).

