For the subset of participants receiving a modified dose of voxelotor as dispersible tablets in this study, AEs will be presented with participants grouped by the dosing form prior to the switch to the modified dose.

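### The SAP gives no paired estimate for the PK switch comparison, and its modified-dose AE summaries have no start at the switch date

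*SAP*

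**What the plan says.** **PK.** Assessing predose whole blood and plasma concentrations in a modified-dose subset is part of the study objectives (Protocol 2; SAP 3). Protocol 8.6 describes the evaluation this way, the day meant being that of the switch: "will be evaluated by comparison of predose voxelotor concentration on 14 Days Post-Switch and 12 Weeks Post-Switch with predose voxelotor concentration on the Day". It adds that "A population pharmacokinetic (PK) analysis may be conducted using nonlinear mixed effects modeling"; the SAP does not mention that model. SAP 8.4 plans two displays:

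- An individual table: "The PK data will be reported for an individual participant with corresponding voxelotor pre-switch dose, pre-switch formulation, and post-switch voxelotor dose".
- Summaries: "the PK data for day of switch, 14-day post-switch, and 12-week post-switch will be summarized (all data and by pre-dose formulation) using descriptive statistics". The listed statistics are the number of valid values, mean, SD, 95% CI, median, minimum and maximum. BLQ values are set to zero.

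SAP 7.2 defines the PK population as "all participants who take at least 1 dose of voxelotor and in whom at least 1 concentration value is reported".

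**AEs.** SAP 8 says that for the "subset of participants receiving the modified dose of voxelotor in dispersible tablet in this study, separate summaries will be provided" for selected data, TEAEs being the example. SAP 8.2.2 adds that for this subset "AEs will be presented with participants grouped by the dosing form prior to the switch to the modified dose". The time rules stated elsewhere are:

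- A TEAE starts at or after initiation of study drug and is counted up to 28 days after discontinuation (SAP 5).
- AEs that began before the first dose are left out of the tables (SAP 8.2.2).
- Partial start dates are resolved against the treatment start date (SAP 6.2.2).

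None of these uses the switch date, although Protocol 5.1 has it recorded on the dosing eCRF. Protocol Appendix B, footnote a, has participants already enrolled switch at a later scheduled visit.

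**The concern.** **PK.** The same participants are sampled at all three times, so the protocol's comparison is naturally a within-participant one. The SAP's intervals belong to single time points and not to the comparison. Because one concentration is enough to enter the PK population, the three summaries can also describe different participants. The expected change depends on the prior formulation, so a combined summary blends two different expectations.

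**AEs.** A table meant to describe the modified dose would, under the stated rules, also hold events from time on the earlier dose. The amount depends on when each participant switched. A reader could take the percentages as experience on the modified dose when much of the observation came before it.

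**Working it through.** The plan states no precision target for the roughly 20 PK participants (SAP 6.1), so there is no figure of its own to reproduce.

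**1. Expected PK ratios, from the documents' doses.** Protocol 5.1, Tables 1 and 2, give modified/original doses of 500/400 = 1.25, 800/600 = 1.33 and 1200/900 = 1.33. The same section reports that "a single dose of the powder for oral suspension had an approximately 35% greater exposure than the same mg dose of dispersible tablets". Assume that exposure is dose-proportional and that predose levels track single-dose exposure.

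- From the original dispersible-tablet dose: post/pre of 1.25 to 1.33.
- From powder: 1.25/1.35 = 0.926 and 1.333/1.35 = 0.988, so 0.93 to 0.99.

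**2. Precision of the comparison.** CV, within-participant correlation r and the 10/10 split by prior formulation are assumptions. Let s = √ln(1 + CV²), giving 0.294, 0.385 and 0.472 for CV 0.3, 0.4 and 0.5. The 95% limits are the estimate multiplied and divided by:

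- Separate summaries treated as independent: exp[t(2n−2) · s · √(2/n)]
- Paired: exp[t(n−1) · s · √(2(1−r)/n)]

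For n = 20 and CV 0.4, unpaired: exp(2.024 × 0.385 × √0.1) = 1.28. Paired with r = 0.5: exp(2.093 × 0.385 × √0.05) = 1.20.

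| n | CV | Unpaired | Paired, r = 0.3 | Paired, r = 0.9 |
|---|---|---|---|---|
| 20 | 0.3 | 1.21 | 1.18 | 1.06 |
| 20 | 0.4 | 1.28 | 1.24 | 1.08 |
| 20 | 0.5 | 1.35 | 1.30 | 1.10 |
| 10 | 0.4 | 1.44 | 1.39 | 1.13 |

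The SAP plans no unpaired ratio. That column is only what a reader could form from the separate summaries.

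**3. Share of AE person-time before the switch** = pre/(pre + post). Follow-up lengths are assumptions.

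| Switch at | 12 weeks after | 48 weeks after |
|---|---|---|
| Day 1 | 0% | 0% |
| Week 12 | 12/24 = 50% | 12/60 = 20% |
| Week 24 | 24/36 = 67% | 24/72 = 33% |
| Week 48 | 48/60 = 80% | 48/96 = 50% |

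**4. Percentage with at least one TEAE**, the SAP's own metric: 1 − exp(−rate × weeks × 7/365.25), with an assumed constant rate that does not change at the switch.

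| Rate per person-year | Weeks after switch | Counted from switch | As written: switch at Week 12 / 24 / 48 |
|---|---|---|---|
| 0.25 | 12 | 5.6% | 10.9 / 15.8 / 25.0% |
| 0.5 | 12 | 10.9% | 20.5 / 29.2 / 43.7% |
| 1 | 12 | 20.5% | 36.9 / 49.8 / 68.3% |
| 0.5 | 48 | 36.9% | 43.7 / 49.8 / 60.1% |

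**The case against.** **PK.** The protocol promises only a comparison. The individual table lets any reader form each paired ratio, the number of valid values is shown at each time point, the study is descriptive, and no decision hangs on an interval. At a correlation of 0.3 the precision gain (1.28 to 1.24) is negligible, and the expected ratios extend a single-dose healthy-volunteer comparison to daily dosing in children. All of this stands as a limit: the point is an improvement and does not expose a contradiction. But a ratio that a reader can work out from a listing is not a planned estimate, and the protocol names this comparison.

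**AEs.** The sponsor may well intend only AEs on the modified dose; the text is silent and does not state that earlier AEs are included. That reading is plausible, but no rule in the SAP produces it, and a programmer applying the written rules would include them. It is also fair that the percentages in step 4 rise purely because observation is longer: under the assumed constant rate, events per person-year do not change. That is the difficulty with a percentage-only table whose start is not the switch and which shows no post-switch time. The number of later switchers, their switch times and the AE rates are unknown, and Day 1 switchers dilute the effect.

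**Remedy.** Imputing day-missing AEs in the switch month to the switch date will move some old-dose events into the table. This is a real cost, but it follows the SAP's own convention at treatment start. Worsening is already part of the SAP's TEAE definition, so using it at the switch adds no new concept.

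**Conclusion.** Both parts hold. SAP 8.4 gives no estimate of the comparison in Protocol 8.6, and the modified-dose AE summaries have no switch-related start, so under the stated rules they take in old-dose AEs from participants who switched after Day 1. This should be changed, but its reach is limited: no primary result or main safety table is affected.

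The PK gain ranges from slight to substantial with the assumed correlation. Its main value is a prespecified answer in the same participants, split by prior formulation. The size of the AE effect rests on assumed switch times, follow-up and rates; that old-dose events enter follows from the written rules. Confidence is medium.

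**What to change.** **SAP 8.4.** Keep the planned displays. For whole blood and plasma, add the within-participant geometric mean ratio (14 days to Day of Switch, and 12 weeks to Day of Switch) with 95% CI, by pre-switch formulation. Include participants with both samples who were taking voxelotor before the switch. State n for each ratio, report BLQ counts per time point, and leave BLQ zeros out of the ratio, since they cannot enter on the log scale. Confirm that the grouping called pre-dose formulation means pre-switch formulation.

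**SAP 8.2.2.** In the modified-dose table, count only AEs with onset or worsening on or after the recorded switch date, by prior dosing form, and show post-switch exposure time.

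**SAP 6.2.2.** Extend the partial-date exception to the switch month. Otherwise the first-of-month rule would place such AEs before the switch.

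A pre-switch column for later switchers is optional and should be labelled descriptive. AE reporting is prompted at the switch (Protocol 5.1.2), PK sites add a 14-day safety visit (Appendix B), and later switchers are those who stayed on study. No before/after contrast should be read as an effect of the switch.

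**Cost.** SAP text and a few tables. Samples, switch date, and pre-switch dose and formulation are already collected. Participants lacking a pair or with BLQ values leave the ratio but stay in the individual table and the summaries. AEs that began before the switch and did not worsen leave this table but stay in the main TEAE tables.

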9. PROTOCOL DEVIATIONS

Protocol deviations as assessed by the study team will be displayed in a data listing and sorted by participant number, and then by date (where applicable) within each participant number. The type of deviation along with a description and any additional comments about the deviation will be listed.
